## 9 Data handling and Monitoring

Data arising from this study is confidential. Identifiable information can only be accessed by delegated members of the study team. Anyone in the research team who will work on Trust premises and see patients, and does not have a substantive contract with NCIC, will need to apply for a letter of access via the NIHR research passport scheme.

Participants will be pseudo anonymised by allocating a study ID to each of them. Patient identifiable data will only be used within North Cumbria Integrated Care NHS Foundation Trust; if applicable, only anonymised data are shared with the wider members of the study team. All identifiable data is stored on password protected NHS computer systems. Anonymised data will be shared and stored using security-enabled systems such as password-protection and encryption of e-mails and files. The requirements of the Data Protection Act and NHS Code of Confidentiality will be followed at all times. All researchers will be fully trained in NHS Confidentiality and GCP training.

All paper data will be held in secure locked environments in the office of the Research & Development department in Cumberland Infirmary, Carlisle, North Cumbria Integrated Care NHS Foundation Trust. Electronic data will be saved on the patient management system such as EMIS, and also a password protected research database. Data released (e.g. by publication) will contain no information that could lead to the identification of an individual participant. Upon completion of the study the site files will be archived for a period of 10 years in line with local archiving policy and procedures.

Direct access to anonymised data only will be granted to authorised representatives from the sponsor, host institution and the regulatory authorities to permit trial-related monitoring, audits and inspections.

Final data, will be shared with Medipin Ltd company in pseudo-anonymised form.

## 10 Governance of study

#### 10.1 APPROVALS

This study will be conducted in compliance with the protocol approved by the Health Research Authority, National Research Ethics Service, and local Trust R&D Approval, and according to Good Clinical Practice standards including the Declaration of Helsinki (1964, Amended Oct 2013). No deviation from the protocol will be implemented without the prior review and approval of the aforementioned review bodies, except where it may be necessary to eliminate an immediate hazard to a research subject. In such case, the deviation will be reported according to policies and procedures.

#### 10.2 SPONSOR & INDEMNITY

North Cumbria Integrated Care NHS Foundation Trust is the sponsor of this study and therefore NHS indemnity applies for design, conduct and management of the study. Medipin Ltd has provided a grant for this study by means of provision of the Medipin test kits free of charge.

Patients will not be given financial incentives for taking part in the study. Travel expenses are not offered in this study since patients are ideally seen when they attend their regular clinical appointment.

## 11 Publication and data-sharing policy

The results of this study will potentially be disseminated through:

- Peer-reviewed scientific journal
- Internal report

A summary of the main findings can be supplied to participants on request and this will be stated in the patient information leaflet.

## Appendix 1, Examples of Monofilament practice variation

#### **Sussex Community NHS:**

Test for neuropathy with a 10g monofilament (neuropathy is present if sensation is lost at any site)

#### Northern Devon and Leicestershire NHS:

The 10 sites to be tested (see figure). Loss of protective sensation = No feeling in less than 8 sites

#### **NHS Borders podiatry service:**

Monofilament testing is the best current method of predicting ulceration due to loss of protective sensation. Test on all five sites in each foot (as per the chart). If the patient feels less than eight applications (in total) of the Monofilament they are considered to have loss of protective sensation.

Loss of protective sensation is a major factor in the aetiology of diabetic foot ulcers.

#### East Lancashire NHS:

Use 10g monofilament and use on the marked sites (apex all toes, 1/3/5 met heads, medial and lateral arch and heel). No problems is 0, any loss of sensation is 1.

## Appendix 1, Case Report Form

Patient Code:

MANDARIN-.....

Researcher completing form: .....

item	outcome	
Patient visit date		
Patient age	Years	
Patient height / weight / BMI	Height (m) Weight (kg) BMI	
Year type II diabetes diagnosed		
Smoking status	Never Ex-smoker Current smoker	
Peripheral Arterial Disease (PAD) recorded in notes	No Yes	
Patient on antihypertensive medication?	No Yes (if yes, which medication?)	
Foot and/or toe malformation recorded in notes	No Yes If yes: - Toes - Foot - Both toes and foot	
Current medication for diabetes	Biguanides (Metformin) Alpha-glucosidase inhibitors (eg acarbose miglitol (Glyset))	
	Dipeptidyl peptidase-4 (DPP-4) inhibitors (eg alogliptin (Nesina), linagliptin (Tradjenta), saxagliptin (Onglyza), sitagliptin (Januvia)	
	Glucagon-like peptide-1 receptor agonists (GLP-1 receptor agonists) (eg dulaglutide (Trulicity), exenatide (Byetta), liraglutide (Saxenda, Victoza) lixisenatide (Adylyxin), semaglutide (Ozempic), tirzepatide (Mounjaro)	
	Meglitinides (eg nateglinide (Starlix), repaglinide (Prandin))	
	Sodium-glucose transporter (SGLT) 2 inhibitors (eg canagliflozin (Invokana), dapagliflozin (Farxiga), empagliflozin (Jardiance), ertugliflozin (Steglatro)	
	Sulfonylureas (eg glimepiride (Amaryl), gliclazide Glipizide, glyburide (Glynase), glyburide-metformin)	

	Thiazolidinediones (eg rosiglitazone, pioglitazone-alogliptin (Oseni))	
	Insulin 
 
rapid- or short-acting insulin.
 
mixed insulin.
 
long-acting insulin.
 
	
Medipin outcome (dorsal, hallux)	Left foot (patient's left foot)	
	
 
Sharp sensation
 
Dull sensation
 
Absent sensation
 
Score if sensation felt (5 being forearm reference score):
 
	
	$\bigcirc 0 & 1 & 2 & 3 & 4 & 5 & 6 & 7 & 8 & 9 & 10 \\ \bigcirc \bigcirc \bigcirc & \bigcirc \bigcirc \bigcirc & \bigcirc \bigcirc \bigcirc & \bigcirc \bigcirc \bigcirc & \bigcirc \bigcirc & \bigcirc \bigcirc & 0 & 0$	
	Right foot 
 
Sharp sensation
 
Dull sensation
 
Absent sensation
 
Score if sensation felt (5 being forearm reference score):
 
	
	$\begin{array}{ c c c c c c c c c c c c c c c c c c c$	
Monofilament 10g (dorsal, hallux)	
 
Left foot (1st application)
 
Present sensation (same or more as forearm)
 
Present sensation (substantially less than forearm)
 
Absent sensation
 
	
	
 
Left foot (2nd application)
 
Present sensation (same or more as forearm)
 
Present sensation (substantially less than forearm)
 
Absent sensation
 
	
	
 
Left foot (3rd application)
 
Present sensation (same or more as forearm)
 
Present sensation (substantially less than forearm)
 
Absent sensation
 
	
	
 
Left foot (4th application)
 
Present sensation (same or more as forearm)
 
Present sensation (substantially less than forearm)
 
Absent sensation
 
	

	
 
Right foot (1st application) 
 
Present sensation (same or more as forearm)
 
Present sensation (substantially less than forearm)
 
Absent sensation
 
 
 
Right foot (2nd application) 
 
Present sensation (same or more as forearm)
 
Present sensation (substantially less than forearm)
 
Absent sensation (substantially less than forearm)
 
 
 

	
 
Right foot (3rd application)
 
Present sensation (same or more as forearm)
 
Present sensation (substantially less than forearm)
 
Absent sensation
 

	Right foot (4 th application) - Present sensation (same or more as forearm) - Present sensation (substantially less than forearm) - Absent sensation
Monofilament 10g (plantar: hallux, third	Left foot
toe, the first metatarsal, the third	Hallux (plantar)
metatarsal, and the fifth metatarsals)	- Present sensation
	- Absent sensation
	- Third toe (plantar)
	- Present sensation
	- Absent sensation
	First metatarsal
	- Absent sensation
	Third metatarsal
	- Present sensation
	- Absent sensation
	Fifth metatarsal
	- Present sensation
	- Absent sensation
	Right foot Hallux (plantar)
	- Present sensation
	- Absent sensation
	- Third toe (plantar)
	- Absent sensation
	First metatarsal
	- Present sensation

	- Absent sensation
	Third metatarsal - Present sensation - Absent sensation Fifth metatarsal - Present sensation - Absent sensation
Michigan Neuropathy Screening Instrument symptom questionnaire completed (yes / no)	
QoL EQ-5D-5L completed (yes / no )	

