#### Medipin test: one application on dorsal side of hallux, proximal to toenail, on both left and right foot

1. Break tab to expose point - avoid contact with fingers.

2. Grasp device between thumb and index finger lightly enough to permit slight axial slippage if required - utilize textured surface to facilitate control.

3. Apply to skin at a perpendicular to standardize point pressure for improved test consistency and optimize annular contact to generate a 'centre surround' field of enhanced acuity. Establish a control area in an unaffected region (forearm) with an 'average' stimulation level by making several quick applications around the same locality for about 5-10 seconds. Press firmly but carefully using a repetitive, percussive contact.

Avoid high amplitude or 'stabbing' actions - penetration is checked by the annulus but never assumed 'impossible'. Instruct your patient this "normal" area represents a 'sharp' sensation and that this equates to a score of 5 out of 10 (on a 10cm scale).

4. With patient's eyes closed, apply the Medipin once to the dorsal area of the great proximal to the nail bed. Ask patient where possible to identify and grade the quantity of deficit between them and the 'control' area. Answer can be no sensation, 'dull' sensation, and 'sharp' sensation. Patient will also score the sensation on a 10cm visual analogue scale.

5. To prevent re-use destroy point by compression against a hard surface and/or dispose of in a biohazard container.

Figure 2. Medipin device.

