#### 8.3 PRIMARY OUTCOME STATISTICS

The Medipin result and monofilament result (either dorsal or plantar outcome) will be presented with descriptive statistics to show percentage of patients with LOPS / DN.

Test	DN Absent	DN Present
10g Monofilament test plantar side, five	Score of 9 or 10 (out of 10)	Score of 8 or lower
plantar locations on both left and right		
foot		
10g Monofilament test: four applications	Score of 3.5 or higher (out of 8).	Score of 3 or lower
on dorsal side of hallux, proximal to	Recognising that score 3.5 to 5	
toenail, on both left and right foot	considered elevated risk of DN in	
	original reference article.	
Medipin test: one application on dorsal	Sensation in both feet (either 'dull'	No sensation in one or
side of hallux, proximal to toenail, on	or 'sharp' sensation, and score of	both feet
both left and right foot	above 0 out of 10)	

Table 6, Definition and score cut-offs for different DN tests (based on published papers).

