#### 8.4 SECONDARY OUTCOME STATISTICS

Evaluation of feasibility that a (Likert) scale can be applied for Medipin in relation to degree of neuropathy, as opposed to standard yes/no quantification and no sensation/dull sensation/sharp sensation distribution. For this, descriptive statistics will be used to present how results are distributed amongst these three outcome modalities. Mann-Whitney U-test will be used to compare median 10-point score between those with present and absent DN respectively (ie yes/no groups), to determine if the median value differs. Similarly, Kruskall-Wallis test will be used to compare median score between the three groups of no sensation/dull sensation/sharp sensation.

Concordance between Medipin and 10g monofilament test results. The binary outcome , DN present or absent, will be used to conduct concordance and distribution comparisons. Cohen's Kappa value will be calculated to assess level of concordance. McNemar's test for paired data will be used to compare distribution of outcomes between Medipin and each 10g monofilament procedure outcome.

Relative performance/concordance achieved with 10g monofilament depending on number of tests and locations included in the assessment. As above for concordance measurement between Medipin outcome and respective 10g monofilament outcomes, the same test is conducted to compare the two different 10g monofilament diagnostic test procedures.

The patient's age, years of diabetes, smoking status, blood pressure medication and diabetes medication, foot malformations, general quality of life (EQ-5Q-DL), and MNSI symptom questionnaire score are primarily used to define the cohort on which the DN screening has been conducted. Parameters collated at the clinic visit will be recorded and presented in a tabulated format. No identifiable data will be presented, only averages and totals.

However, binary logistic regression may be applied to evaluate if any parameters are associated with Medipin positive tests, with the the Medipin result being the dependent variable. Likewise, this regression analysis can also be used with either of the monofilament test outcomes as the dependent. This will then allow comparison of variables associated with small fibre and large fibre screening. This type of analysis may only be feasible with the potential larger sample size outlined in Section 8.2 of this protocol. Odds ratios (logistic) will be expressed as Beta with 95% confidence intervals.

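### The case report form asks for a Medipin score only when the prick is felt, yet section 8.4 tests that score in groups defined by not feeling it

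*Protocol*

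**What the plan says.** Four places in the protocol bear on what is recorded when the patient does not feel the Medipin.

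- **Section 5.3, Medipin test, step 4.** After the no/dull/sharp answer, "Patient will also score the sensation on a 10cm visual analogue scale". There is no condition, and no value is given for an unfelt prick.
- **Appendix 1, Case Report Form.** For each foot there are three tick options, one of them "Absent sensation". A 0 to 10 row follows, introduced by "Score if sensation felt (5 being forearm reference score"). The condition is printed for the left foot and again for the right.
- **Section 8.3, Table 6.** Medipin DN present is "No sensation in one or" both feet. DN absent requires dull or sharp sensation in both feet and a score "above 0 out of 10".
- **Section 8.4.** "Mann-Whitney U-test will be used to compare median 10-point score between those with present and absent DN respectively", and the "Kruskall-Wallis test will be used to compare median score between the three groups of no sensation/dull sensation/sharp sensation".

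Section 5.6 names the case report form as source data for the test results, and section 5.4 confines each participant to one visit.

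**The concern.** Section 2.2 asks whether a 10-point scale can express the degree of neuropathy rather than only its presence. Both tests in section 8.4 need scores from feet, or patients, with no sensation. The form that captures the data tells staff to skip the score in that case. If they follow it, the severe end of the scale is not observed, and the planned tests either cannot be run as described or compare something else. An analysis plan written later cannot supply a patient-given score that was not taken at the visit.

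**Working it through.** **1. Sample size, reproduced.** Inputs from section 8.2: prevalence 10%, 95% confidence, precision 5%, population 160,000. n0 = 1.96² × 0.10 × 0.90 / 0.05² = 138.29. With the finite-population correction, n = n0 / (1 + (n0 − 1)/160,000) = 138.17, rounded up to 139. At 2.5% precision n0 = 553.17 and n = 551.27, rounded up to 552. Both match the protocol. Expected positives are 0.10 × 139 = 13.9, about 14, and 0.10 × 552 = 55.2, about 55. At the roughly 20% prevalence that section 8.2 cites from the literature, 0.20 × 139 = 27.8, about 28.

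**2. Kruskal-Wallis, by foot.** The three categories are recorded per foot. A foot ticked absent has no score, so that group has size 0. The statistic contains a term R²/n for each group and is undefined when n = 0; a trial run with one empty group returned no value. Only dull versus sharp can be compared.

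**3. Mann-Whitney, by patient.** I read DN present here as the Medipin result, since the sentence belongs to the Medipin scale objective. There is one application per foot, hence at most two scores per patient. A patient with loss in both feet has none. A patient with one-sided loss has one, from the foot that felt the prick. Patients with any score = positives × (1 − share with loss in both feet). The protocol does not give that share, so it is shown as an assumed range:

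| Share with loss in both feet | 14 positive of 139 | 28 positive of 139 | 55 positive of 552 |
|---|---|---|---|
| 25% | 10.5 | 21 | 41.25 |
| 50% | 7 | 14 | 27.5 |
| 75% | 3.5 | 7 | 13.75 |
| 90% | 1.4 | 2.8 | 5.5 |
| 100% | 0 | 0 | 0 |

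**4. What if an unfelt prick is coded 0?** Take 14 DN-present patients, each with a patient-level score of 0 (all with loss in both feet, or scored by the worse foot). The 125 DN-absent patients all score above 0, because Table 6 requires it. Separation is complete: U = 0 against an expected 14 × 125 / 2 = 875, with standard deviation √(14 × 125 × 140 / 12) = 142.9, so z = 6.12 and the two-sided p is below 10⁻⁹. In 500 simulated sets (14 zeros; 125 scores drawn from 1 to 10; dull and sharp labels assigned at random, unrelated to the score), the largest Mann-Whitney p was 7.9 × 10⁻¹⁰ and the largest Kruskal-Wallis p was 6.1 × 10⁻⁹. The tests reject whether or not the scale carries information among feet that feel the prick.

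**The case against.** The strongest reply is that 0 was meant for an unfelt prick. Table 6 pairs DN absent with a score above 0, the printed row starts at 0, and the companion dorsal monofilament test in section 5.3 scores an unperceived stimulus as 0. The absent tick is always captured, so a blank beside it could be filled by one coding sentence. That stands in part. The gap is an unresolved conflict about coding, and a reader who infers that the data are irretrievably lost goes further than the documents allow. But no passage says to record or impute 0, the form's condition points the other way, and step 4 of the working shows that a rule-based 0 gives a test of the definition, not of the scale.

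A second reply is that the no-sensation group is empty only by foot. That is correct. Section 8.4 does not fix the unit of analysis; if patients were grouped by their worse foot, one-sided patients would bring a score into that group. It would come from the foot that felt the prick, so the group would not represent absent sensation.

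A reader might also infer a definite loss of power. The documents do not support one: they give no left-right correlation, no score distribution and no effect size, so any power figure would rest on an invented score model.

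Finally, this is a secondary feasibility objective that section 8.4 addresses first with descriptive distributions. That is true and limits the reach of the point.

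**Conclusion.** The point holds as a conflict within the current protocol text. As printed, the foot-level Kruskal-Wallis test has an empty group. The Mann-Whitney DN-present group is reduced to the sensate foot of one-sided patients: about 10 patients at most of 14 over the range shown, and possibly none. Those counts rest on the protocol's 10% prevalence and on an assumed share with loss in both feet; the conflict itself rests on neither. Reading 0 into the blanks would not rescue the tests.

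It would be wrong to infer that the main results are at risk. The primary detection rate, Cohen's kappa and McNemar's test use the present/absent result, and the sensation category behind it is recorded for every foot. The matter should be settled before recruitment, because each patient is seen once.

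**What to change.** Reconcile section 5.3 step 4, Table 6, section 8.4 and the case report form on what is recorded for an unfelt prick. Either route works.

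- **(a) Score every foot.** Remove the condition from the form so that the patient gives a score for each foot, 0 allowed. State in section 8.4 that any score set to 0 by rule is reported descriptively and not tested against the category that defines it. Table 6 should then also say how a felt prick marked 0 is classified, since at present it fits neither column.
- **(b) Keep the skip rule.** Drop the no-sensation group from the test in section 8.4, leaving dull versus sharp. Report the DN-present versus DN-absent scores descriptively, stating that the DN-present scores come only from the sensate foot of patients with one-sided loss.

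Under either route, state whether the unit of analysis is the foot or the patient.

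The cost is small. Route (a) changes one line of the form for each foot and adds a sentence each to section 8.4 and Table 6, and some patients may find it odd to score a stimulus they did not feel. Route (b) means one fewer hypothesis test.

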## Appendix 2, Study participant flowchart

## Appendix 3, Quality of life: EQ-5D-5L

	The best heal	th
Under each heading, please tick the ONE box that best describes your health	you can imagi TODAY	ne
MOBILITY	Ŧ	100
I have no problems in walking about	⊒	95
I have slight problems in walking about	먁	00
I have moderate problems in walking about		90
I have severe problems in walking about	哇	85
I am unable to walk about	υŧ	
	+	80
SELF-CARE	重	75
I have no problems washing or dressing myself	οŦ	
I have slight problems washing or dressing myself	∓	70
I have moderate problems washing or dressing myself	οŦ	65
I have severe problems washing or dressing myself	正	05
I am unable to wash or dress myself	.œ‡–	60
USUAL ACTIVITIES (e.g. work study housework family or leisure activities)	重	55
I have no problems doing my usual activities	ьŦ	
I have slight problems doing my usual activities		50
I have moderate problems doing my usual activities	οŦ	45
I have severe problems doing my usual activities	ΞŦ	40
I am unable to do my usual activities	- 1 -	40
	Ŧ	
PAIN / DISCOMFORT	Ŧ	35
I have no pain or discomfort		30
I have slight pain or discomfort		00
I have moderate pain or discomfort	υŦ	25
I have severe pain or discomfort	υŦ	
I have extreme pain or discomfort	·=	20
ANXIETY / DEPRESSION	Ŧ	15
I am not anxious or depressed	υŦ	10
I am slightly anxious or depressed		10
I am moderate anxious or depressed	υŦ	5
I am severely anxious or depressed	υŦ	
I am extremely anxious or depressed	±	0

©EuroQoL Group 1990

- We would like to know how good or bad your health is **TODAY**.
- This scale is numbered from **0** to **100**.
- **100** means the best health you can imagine.
  - 0 means the worst health you can imagine
- Mark an **X** on the scale to indicate how your health is **TODAY**.
- Now, please write the number you marked on the scale in the box below

YOUR HEALTH TODAY =

©EuroQoL Group 1990

# Appendix 4, Michigan Neuropathy Screening Instrument symptom questionnaire

#### MNSI symptom questionnaire

1. Are your legs and/or feet numb?	Yes / No
2. Do you ever have any burning pain in your legs and/or feet?	Yes / No
3. Are your feet too sensitive to touch?	Yes / No
4. Do you get muscle cramps in your legs and/or feet?	Yes / No
5. Do you ever have any prickling feelings in your legs or feet?	Yes / No
6. Does it hurt when the bed covers touch your skin?	Yes / No
7. When you get into the bath or shower, can you tell hot water from cold water?	Yes / No
8. Have you ever had an open sore (ulcer) on your foot?	Yes / No
9. Has your doctor ever told you that you have diabetic neuropathy?	Yes / No
10. Do you feel weak all over most of the time?	Yes / No
11. Are your symptoms worse at night?	Yes / No
12. Do your legs hurt when you walk?	Yes / No
13. Are you able to sense your feet when you walk?	Yes / No
14. Is the skin on your feet so dry that it cracks open?	Yes / No
15. Have you ever had a (toe/foot/leg) amputation?	Yes / No

Total number of reported symptoms based on composite score of MNSI symptom questionnaire "yes" responses, with questions 7 and 13 reverse-scored.

From Ylitalo et al (2013):

Questions 1, 8, 13, and 15 are considered indicators of large fibre nerve dysfunction.

Questions 2, 3, 5, 6, 7, and 14 are considered indicators of small fibre nerve dysfunction
